3.3 Visit 2 (Treatment Periods 1, 2, and 3)

3.3.1 Period 1

Subjects will report to the CRU on the morning of Day 1.

3.3.1.1 Day 1

- Review of medical history;
- Review of medications and supplements;
- Measurement of vital signs (weight, seated SBP/DPB, and heart rate);

- Provide the first dose of single-blind placebo at least 45 minutes prior to breakfast;
- Provide breakfast;
- Subjects will be fitted with the continuous glucose monitoring (CGM) device and data recording will begin;
- Provide 4 doses (8 capsules) of single-blind placebo and instruct subjects to take one dose at least 45 minutes before lunch, one dose at bedtime, one dose at least 45 minutes before breakfast on Day 2, and one dose at least 45 minutes before lunch on Day 2.
- Adverse events will be monitored and recorded.
- Subjects will be instructed to return to the CRU at approximately 5pm (± 30 minutes) on Day 2.

3.3.1.2 Day 2

- Admission to the CRU at approximately 5pm (± 30 minutes);
- Review of medications and supplements;
- Measurement of vital signs (weight, seated SBP/DPB, heart rate, and temperature);
- Perform breathalyzer;
- Collect a urine sample for:
 - Drug screen;
 - Pregnancy testing (WCBP only)
- Provide a standardized diabetic meal at approximately 7pm (± 60 minutes). Standardized meals will continue throughout the remainder of the study Period.
- Provide a dose of single-blind placebo at approximately 10pm (± 60 minutes).
- Continue CGM monitoring;
- Adverse events will be monitored and recorded.

3.3.1.3 Day 3

- Review of medications and supplements;
- Measurement of vital signs (weight, seated SBP/DPB, heart and rate);
- Provide a dose of single-blind placebo at approximately 7am (± 60 minutes);
- Provide breakfast no sooner than 45 minutes after the morning dose;
- Provide a dose of single-blind placebo at approximately 1pm (± 60 minutes), at least 45 minutes prior to lunch;
- Provide lunch no sooner than 45 minutes after the afternoon dose;

- Provide dinner at approximately 7pm (\pm 60 minutes);
- Provide a dose of single-blind placebo at approximately 10pm (\pm 60 minutes);
- Collect a blood sample according to schedule (per randomization scheme, either morning, afternoon, or evening) prior to the specified dose of placebo for:
 - Pre-dose PD analysis
 - Serum chemistry
- Collect scheduled (per randomization scheme) postdose PD blood draws every 30 minutes (\pm 5 minutes) until 5 hours has elapsed;

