- Replace the CGM cannula at approximately 7pm (\pm 60 minutes), such that it does not interfere with any post-dose PD blood draws;
- Adverse events will be monitored and recorded.

3.3.1.4 Day 4

- Review of medications and supplements;
- Measurement of vital signs (weight, seated SBP/DPB, and heart rate);
- Randomization
- Provide a dose of study treatment or placebo at approximately 7am (\pm 60 minutes);
- Provide breakfast no sooner than 45 minutes after the morning dose;
- Provide a dose of study treatment or placebo at approximately 1pm (\pm 60 minutes), at least 45 minutes prior to lunch;
- Provide lunch no sooner than 45 minutes after the afternoon dose;
- Provide dinner at approximately 7pm (\pm 60 minutes);
- Provide a dose of study treatment or placebo at approximately 10pm (\pm 60 minutes);
- Continue CGM monitoring;
- Adverse events will be monitored and recorded.

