3.6 Schedule of Events

Table 1 below describes the daily schedule of events from Screening Visit 1 through Follow-Up Visit 3.

Table 1: Daily Schedule of Events from Screening Through Follow-Up Visit

Visit	Screening Visit 1	Treatment Visit 2 Periods 1, 2, and 3										Follow-Up Visit 3	EW		
		Study Day	Day -7 to -10	1	2	3	4	5	6	7	8			9	10
Informed Consent	X														
Medical History	X	X													
Demographics	X														
Concomitant Medications	X	X	X	X	X	X	X	X	X	X	X	X	X	X	X
Inclusion/Exclusion Criteria	X														
Physical Exam	X												X	X	
ECG	X														
Vital Signs ¹	X	X	X	X	X	X	X	X	X	X	X	X	X	X	
Hematology/Chemistry/Urinalysis ²	X ²			X ²						X ²			X ²	X ²	
Urine Drug Screen	X		X												
Breathalyzer	X		X												
Serum Pregnancy Test ³	X														
Urine Pregnancy Test ³			X												
Placebo Administration ⁴		X	X	X							X				
CGM Monitoring ⁵		X	X	X	X	X	X	X	X	X	X				
CRU Admission			X												
Standardized Diabetic Meals ⁶		X	X	X	X	X	X	X	X	X	X				
Pharmacodynamic Samples ⁷				X					X						
Remove CGM and Download Data											X				
Randomization/Crossover ⁸					X										
Treatment Administration ⁹					X	X	X	X	X						
CRU Discharge											X				
Adverse Events		X	X	X	X	X	X	X	X	X	X	X	X	X	
Study Disposition												X	X		

- ¹Vital signs include height, weight, heart rate, systolic BP, and diastolic BP. Height will be measured at Screening only. Temperature will be measured at Visit 2/Day 2 only, prior to admission.
- ²Screening labs will include standard hematology/chemistry/urinalysis, plus HbA_{1c}, C-peptide, and TSH. FSH will also be performed for women who are pre-menopausal. On Visit 2 Days 3 and 8, chemistry analysis will be performed without hematology or urinalysis. Visit 3 and EW labs will include standard hematology/chemistry/urinalysis.
- ³Pregnancy tests will be performed for women of childbearing potential only.
- ⁴A single dose of placebo will be administered on the morning of Day 1. Subjects will be dispensed the next 4 doses (8 capsules) with dosing instructions. On Day 3 and Day 9, doses will be administered at approximately 7am (±60 minutes), 1pm (±60 minutes), and 10pm (±60 minutes).
- ⁵The CGM monitor will be fitted on Day 1, the cannula will be changed on Day 3 at approximately 7pm (±60 minutes), and the monitor will continue recording measurements until the morning of Day 10.

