6.4 Efficacy Assessments

6.4.1 Continuous Glucose Monitors (CGM)

A continuous glucose monitor (CGM) will be used to monitor patient glucose levels (including post-prandial) during Visit 2, Periods 1, 2, and 3. Further information about the device can be found in the laboratory manual.

Subjects will have the CGM implanted on Day 1 of each treatment Period. On Day 3, the cannula will be changed and the CGM will be re-implanted to collect data until the morning of Day 10. Staff will be advised regarding appropriate procedures in the event of nocturnal hypoglycemia.

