2.8. Efficacy Evaluations

2.8.1. Continuous Glucose Monitoring

The last 2 days with at least 80% of expected measurements prior to dosing will be considered the run-in days for each of the parameters. The last 2 days with at least 80% of expected measurements prior to 8 hours after the last dose will be considered the on treatment days. The measurements more than 8 hours after the last dose will be considered the follow-up days.

The 24-hr period (6AM to 6AM), nighttime (from 10pm to 6am), daytime (6AM to 10PM), and post-prandial (first hour after meal start time including breakfast, lunch, and dinner) glucose values will be summarized. The mean, standard deviation, minimum, maximum, first quartile, median, third quartile and inner-quartile range will be presented.

The area under the curve (AUC) will be derived for each of the time periods (24-hour, daytime and nighttime) using the indicated days (run-in days, treatment days and follow-up days). The average glucose measurement will be derived by dividing the AUC by the number of observed hours. The average change from run-in will be derived for each treatment regimen for both the treatment days and the follow-up days.

The placebo adjusted change in means will be derived for each of the active therapy regimens by subtracting the placebo mean (the mean change from run-in while the subject was receiving placebo) from the active therapy mean (the mean change from run-in while the subject was receiving the active therapy).

The placebo adjusted change in means will be derived for both the treatment days and the follow-up days. The placebo adjusted change in means will be analyzed using an Analysis of Variance (ANOVA) with treatment as the main effect to determine whether multiple doses a day has an effect on the CGM parameters. If the residuals are not normally distributed, then a Kruskal-Wallis test (one-way analysis of variance on the ranks) will be performed.

The ratios of the placebo adjusted change in means between the active treatments within each subject will also be derived to estimate the magnitude of the dose response.

Summary statistics will be presented for both the placebo adjusted change in means and the ratios of the placebo adjusted change in means. Analysis results will be presented for the change in means.

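### On Day 3 of every period the CGM cannula is replaced at the dinner hour, which usually compromises one of the two standardized run-in dinners

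*Protocol*

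**What the plan says.** - **Day 3 procedures (Protocol 3.3.1.3, repeated for Periods 2 and 3).** One item is "Provide dinner at approximately 7pm" and another is "Replace the CGM cannula at approximately 7pm", each ±60 minutes. The replacement has one condition: "such that it does not interfere with any post-dose PD blood draws". Footnote 5 in Protocol 3.6 repeats the time: "the cannula will be changed on Day 3 at approximately 7pm".
- **What the replacement involves (Protocol 6.4.1).** "On Day 3, the cannula will be changed and the CGM will be re-implanted to collect data until the morning of Day 10". No replacement is therefore planned on Day 8, when dinner is again at about 7pm.
- **The other run-in dinner (Protocol 3.3.1.2).** On Day 2: "Provide a standardized diabetic meal at approximately 7pm". The first sensor is still in place.
- **Analysis (SAP 2.8.1).** "post-prandial (first hour after meal start time including breakfast, lunch, and dinner) glucose values will be summarized". Run-in is the last two days before dosing with at least 80% of expected readings. Average glucose is the AUC divided by the number of observed hours.
- **Gaps (SAP 2.13).** The only filling allowed is linear interpolation for the trapezoidal areas.

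Neither document gives the time the device needs to restart, or a rule for readings just after insertion.

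**The concern.** The schedule sequences the replacement around blood draws but not around the meal. At nominal times the sensor is out, or newly inserted, exactly when the post-dinner hour begins. The matching hour on Day 8 is undisturbed, so run-in and end of treatment are not measured alike.

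Three results are exposed: the post-prandial summaries, which serve a secondary objective; the counts of subjects with at least one reading above each threshold (SAP 2.7.7), where a missed post-dinner peak can lower the run-in count; and the change from run-in derived for each regimen in daytime and 24-hour glucose.

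Day 3 also carries particular weight. The 24-hour and daytime objectives and table titles name it as the pre-treatment day. Standardized meals become continuous only from dinner on Day 2, so Day 3 is the only run-in day eaten wholly in the unit.

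**Working it through.** The plan gives no figure of its own to reproduce. The check uses its clock times and stated assumptions.

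**1. How often the dinner hour is hit.** Let D be replacement time minus dinner start, in minutes. Both windows are 6pm to 8pm. Assume the two times are independent and uniform, so D is triangular on −120 to +120, with F(x) = (120 + x)²/28,800 for x ≤ 0 and F(x) = 1 − (120 − x)²/28,800 for x > 0. Let g be the minutes without readings after replacement (assumed). The hour is interrupted or overlapped when −g < D < 60, so P = F(60) − F(−g), with F(60) = 1 − 60²/28,800 = 0.875.

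| g (min) | F(−g) | P | Mean minutes lost of 60 |
|---|---|---|---|
| 0 | 0.500 | 37.5% | 0 |
| 30 | 0.281 | 59.4% | 12.5 |
| 60 | 0.125 | 75.0% | 25.0 |
| 120 | 0 | 87.5% | 40.0 |

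Simulation agrees. In 1 − 0.875 = 12.5% of cases the replacement comes more than an hour after dinner starts and the hour is untouched. At nominal times (D = 0), a 30-minute gap removes half the hour and a gap of 60 minutes or more removes all of it.

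**2. Whether the 80% rule catches it.** The rule tolerates 0.20 × 24 = 4.8 h over 24 hours and 0.20 × 16 = 3.2 h in daytime. A 1 to 2 h gap leaves 95.8% to 91.7% of the 24-hour day and 93.8% to 87.5% of daytime, so Day 3 still qualifies for both. If the rule is applied to the three post-prandial hours together, losing dinner leaves 2/3 = 66.7% and the day fails. The SAP does not say whether the rule is applied that way.

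**3. Effect on the run-in mean if the gap is left out.** Let e be the excess of glucose in the gap over the mean of the recorded hours. The run-in mean is low by gap hours × e / window hours.

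| | Day 3 alone | Two-day run-in |
|---|---|---|
| 24-hour, 1 h, e = 30 mg/dL | 30/24 = 1.25 | 30/48 = 0.6 |
| 24-hour, 2 h, e = 60 mg/dL | 120/24 = 5.0 | 120/48 = 2.5 |
| Daytime, 1 h, e = 30 mg/dL | 30/16 = 1.9 | 30/32 = 0.9 |
| Daytime, 2 h, e = 60 mg/dL | 120/16 = 7.5 | 120/32 = 3.75 |

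The run-in is two days, so the right-hand column applies.

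**4. The direction is not fixed.** A replacement before dinner can remove low pre-meal readings, which raises the run-in mean. Interpolation across the gap usually shrinks the shift. If the area is interpolated across a 2 h gap (SAP 2.13) but divided only by observed hours (SAP 2.8.1), that day's 24-hour mean is inflated by 24/22, about 9%. The two sections do not say that area and denominator cover the same interval.

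**5. Whether placebo adjustment removes it.** The collision recurs in the placebo period, so the average shift largely cancels. One group is less certain. Protocol 5.2 gives each subject one morning, one afternoon and one evening sampling period, with qd always evening and bid morning or evening. A subject on qd and bid must then have bid in the morning and placebo in the afternoon. Afternoon draws end 5 h after a dose given between noon and 2pm, so between 5pm and 7pm. They can block the first half of the 6pm to 8pm replacement window in the placebo period but in neither active period.

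**The case against.** The strongest reply is that the planned analysis absorbs the problem. The run-in is two days, and the Day 2 dinner is standardized and read by an undisturbed sensor. The modelled endpoint is the within-subject placebo-adjusted change, and the same replacement occurs under placebo. The post-prandial objective and Table 14.2.4.1 name no baseline day. The gap length and glucose excess are assumptions, and the laboratory manual, to which Protocol 6.4.1 refers for the device, may cover restart and post-insertion readings. The trial is also declared not powered for statistical significance.

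Most of this stands and limits the point. A reader might infer that the baseline dinner hour is lost in every subject and period, and that every regimen's change is pushed upwards by 1.25 to 5.0 mg/dL. The documents do not support that: the windows leave some dinners untouched, Day 2 supplies a second dinner, and both the size and the direction depend on where the gap falls and how it is filled. Replacing the sensor before randomized dosing is also defensible, since Days 4 to 8 are then read by one sensor.

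The reply does not reach results outside the placebo-adjusted model. Post-prandial glucose receives summary statistics only, the threshold counts have no placebo adjustment, and the change from run-in is also derived by regimen. Cancellation is also not assured for qd-plus-bid subjects.

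**Conclusion.** The scheduling conflict is real and recurs in all three periods. Followed as written, the plan interrupts the Day 3 post-dinner hour, or places it in the gap after replacement, at nominal times and in 37.5% to 87.5% of cases across the windows. Those percentages rest on uniform, independent timing and an assumed gap of 0 to 120 minutes.

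One of only two standardized run-in dinners is compromised; the whole baseline is not removed. With an unfilled 1 to 2 h gap and an excess of 30 to 60 mg/dL, both assumed, the two-day run-in mean is low by about 0.6 to 2.5 mg/dL (24-hour) or 0.9 to 3.75 mg/dL (daytime). Other gap handling could shrink or reverse this. Most of it cancels in the placebo-adjusted change. The exposure that remains is in the post-prandial summaries, the run-in threshold counts and the per-regimen changes. Severity is minor.

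**What to change.** **Protocol, Day 3 procedures in each period.** State that the cannula replacement must not fall in the first hour after dinner starts. For example, serve dinner early in its window, make the replacement at least 60 minutes after dinner starts and after the last afternoon PD draw, still within 7pm ±60 minutes, and serve dinner at the same clock time on Day 8. A 6pm dinner leaves 7pm to 8pm for the replacement. The opposite order, with the replacement at 6pm before a late dinner, is less safe because afternoon draws may run to 7pm.

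**SAP 2.8.1.** Use a post-prandial hour only if it is fully recorded. Compute each change from run-in on clock hours observed on both the run-in and the on-treatment days, with the area and its hour denominator covering the same interval. This is still needed after re-sequencing, because the gap remains in the daytime and 24-hour means. It also helps if conduct can no longer be changed.

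**Cost.** A slightly tighter evening schedule on Days 3 and 8, and a little more programming. No procedure is added. After a late afternoon dose, an early dinner may precede the last PD draw. The present windows already allow this.

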3.3.1.5 Days 5-7

- Review of medications and supplements;
- Measurement of vital signs (weight, seated SBP/DPB, and heart rate);
- Provide a dose of study treatment or placebo at approximately 7am (\pm 60 minutes);
- Provide breakfast no sooner than 45 minutes after the morning dose;
- Provide a dose of study treatment or placebo at approximately 1pm (\pm 60 minutes);

- Provide lunch no sooner than 45 minutes after the afternoon dose;
- Provide dinner at approximately 7pm (\pm 60 minutes);
- Provide a dose of study treatment or placebo at approximately 10pm (\pm 60 minutes);
- Continue CGM monitoring;
- Adverse events will be monitored and recorded.

3.3.1.6 Day 8

- Review of medications and supplements;
- Measurement of vital signs (weight, seated SBP/DPB, and heart rate);
- Provide a dose of study treatment or placebo at approximately 7am (\pm 60 minutes);
- Provide breakfast no sooner than 45 minutes after the morning dose;
- Provide a dose of study treatment or placebo at approximately 1pm (\pm 60 minutes);
- Provide lunch no sooner than 45 minutes after the afternoon dose;
- Provide dinner at approximately 7pm (\pm 60 minutes);
- Provide a dose of study treatment or placebo at approximately 10pm (\pm 60 minutes);
- Collect a blood sample according to schedule (per randomization scheme, either morning, afternoon, or evening) prior to the specified dose of placebo for:
 - Pre-dose PD analysis
 - Serum chemistry
- Collect scheduled (per randomization scheme) postdose PD blood draws every 30 minutes (\pm 5 minutes) until 5 hours has elapsed;
- Continue CGM monitoring;
- Adverse events will be monitored and recorded.

3.3.1.7 Day 9

- Review of medications and supplements;
- Measurement of vital signs (weight, seated SBP/DPB, and heart rate);
- Provide a dose of single-blind placebo at approximately 7am (\pm 60 minutes);
- Provide breakfast no sooner than 45 minutes after the morning dose;
- Provide a dose of single-blind placebo at approximately 1pm (\pm 60 minutes);
- Provide lunch no sooner than 45 minutes after the afternoon dose;

- Provide dinner at approximately 7pm (\pm 60 minutes);
- Provide a dose of single-blind placebo at approximately 10pm (\pm 60 minutes);
- Continue CGM monitoring;
- Adverse events will be monitored and recorded.

3.3.1.8 Day 10

- Review of medications and supplements;
- Measurement of vital signs (weight, seated SBP/DPB, and heart rate);
- Remove the CGM monitor; download CGM data;
- Provide breakfast;
- Adverse events will be monitored and recorded.
- Subjects will be discharged for a minimum 2-week washout period.

3.3.2 Period 2

Subjects will report to the CRU on the morning of Day 1.

3.3.2.1 Day 1

- Review of medical history;
- Review of medications and supplements;
- Measurement of vital signs (weight, seated SBP/DPB, and heart rate);
- Provide the first dose of single-blind placebo at least 45 minutes prior to breakfast;
- Provide breakfast;
- Subjects will be fitted with the continuous glucose monitoring (CGM) device and data recording will begin;
- Provide 4 doses of single-blind placebo and instruct subjects to take one dose at least 45 minutes before lunch, one dose at bedtime, one dose at least 45 minutes before breakfast on Day 2, and one dose at least 45 minutes before lunch on Day 2.
- Adverse events will be monitored and recorded.
- Subjects will be instructed to return to the CRU at approximately 5pm (\pm 30 minutes) on Day 2.

3.3.2.2 Day 2

- Admission to the CRU at approximately 5pm (\pm 30 minutes);
- Review of medications and supplements;

- Measurement of vital signs (weight, seated SBP/DPB, heart rate, and temperature);
- Perform breathalyzer;
- Collect a urine sample for:
 - Drug screen;
 - Pregnancy testing (WCBP only)
- Provide a standardized diabetic meal at approximately 7pm (\pm 60 minutes). Standardized meals will continue throughout the remainder of the study Period.
- Provide a dose of single-blind placebo at approximately 10pm (\pm 60 minutes).
- Continue CGM monitoring;
- Adverse events will be monitored and recorded.

3.3.2.3 Day 3

- Review of medications and supplements;
- Measurement of vital signs (weight, seated SBP/DPB, heart and rate);
- Provide a dose of single-blind placebo at approximately 7am (\pm 60 minutes);
- Provide breakfast no sooner than 45 minutes after the morning dose;
- Provide a dose of single-blind placebo at approximately 1pm (\pm 60 minutes), at least 45 minutes prior to lunch;
- Provide lunch no sooner than 45 minutes after the afternoon dose;
- Provide dinner at approximately 7pm (\pm 60 minutes);
- Provide a dose of single-blind placebo at approximately 10pm (\pm 60 minutes);
- Collect a blood sample according to schedule (per randomization scheme, either morning, afternoon, or evening) prior to the specified dose of placebo for:
 - Pre-dose PD analysis
 - Serum chemistry
- Collect scheduled (per randomization scheme) postdose PD blood draws every 30 minutes (\pm 5 minutes) until 5 hours has elapsed;
- Replace the CGM cannula at approximately 7pm (\pm 60 minutes), such that it does not interfere with any post-dose PD blood draws;
- Adverse events will be monitored and recorded.

3.3.2.4 Day 4

- Review of medications and supplements;
- Measurement of vital signs (weight, seated SBP/DPB, and heart rate);
- Randomization
- Provide a dose of study treatment or placebo at approximately 7am (\pm 60 minutes);
- Provide breakfast no sooner than 45 minutes after the morning dose;
- Provide a dose of study treatment or placebo at approximately 1pm (\pm 60 minutes), at least 45 minutes prior to lunch;
- Provide lunch no sooner than 45 minutes after the afternoon dose;
- Provide dinner at approximately 7pm (\pm 60 minutes);
- Provide a dose of study treatment or placebo at approximately 10pm (\pm 60 minutes);
- Continue CGM monitoring;
- Adverse events will be monitored and recorded.

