3.3.2.5 Days 5-7

- Review of medications and supplements;
- Measurement of vital signs (weight, seated SBP/DPB, and heart rate);
- Provide a dose of study treatment or placebo at approximately 7am (\pm 60 minutes);
- Provide breakfast no sooner than 45 minutes after the morning dose;
- Provide a dose of study treatment or placebo at approximately 1pm (\pm 60 minutes);
- Provide lunch no sooner than 45 minutes after the afternoon dose;
- Provide dinner at approximately 7pm (\pm 60 minutes);
- Provide a dose of study treatment or placebo at approximately 10pm (\pm 60 minutes);
- Continue CGM monitoring;
- Adverse events will be monitored and recorded.

3.3.2.6 Day 8

- Review of medications and supplements;
- Measurement of vital signs (weight, seated SBP/DPB, and heart rate);
- Provide a dose of study treatment or placebo at approximately 7am (\pm 60 minutes);
- Provide breakfast no sooner than 45 minutes after the morning dose;

- Provide a dose of study treatment or placebo at approximately 1pm (\pm 60 minutes);
- Provide lunch no sooner than 45 minutes after the afternoon dose;
- Provide dinner at approximately 7pm (\pm 60 minutes);
- Provide a dose of study treatment or placebo at approximately 10pm (\pm 60 minutes);
- Collect a blood sample according to schedule (per randomization scheme, either morning, afternoon, or evening) prior to the specified dose of placebo for:
 - Pre-dose PD analysis
 - Serum chemistry
- Collect scheduled (per randomization scheme) postdose PD blood draws every 30 minutes (\pm 5 minutes) until 5 hours has elapsed;
- Continue CGM monitoring;
- Adverse events will be monitored and recorded.

3.3.2.7 Day 9

- Review of medications and supplements;
- Measurement of vital signs (weight, seated SBP/DPB, and heart rate);
- Provide a dose of single-blind placebo at approximately 7am (\pm 60 minutes);
- Provide breakfast no sooner than 45 minutes after the morning dose;
- Provide a dose of single-blind placebo at approximately 1pm (\pm 60 minutes);
- Provide lunch no sooner than 45 minutes after the afternoon dose;
- Provide dinner at approximately 7pm (\pm 60 minutes);
- Provide a dose of single-blind placebo at approximately 10pm (\pm 60 minutes);
- Continue CGM monitoring;
- Adverse events will be monitored and recorded.

3.3.2.8 Day 10

- Review of medications and supplements;
- Measurement of vital signs (weight, seated SBP/DPB, and heart rate);
- Remove the CGM monitor; download CGM data;
- Provide breakfast;

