5.2 Randomization

This is a single center, randomized, double-blind, 3-way crossover study. Approximately 30 eligible subjects will be randomized to placebo and 2 of the 3 possible dose groups: ORMD-0801 460 IU qd (in the evening), ORMD-0801 460 IU bid (in the morning and evening) and ORMD-0801 460 IU tid (morning, afternoon, and evening).

In order to estimate the morning, afternoon, and evening PD effect, each subject will have one period in which the PD blood samples are drawn in the morning, one period in which the PD blood samples are drawn in the afternoon and one period in which the PD blood samples are drawn in the evening. When the subject is on active therapy, the PD blood samples will be drawn after an active therapy dose (not after the placebo dummy). Thus, if the subject is taking ORMD-0801 460 IU qd, the PD blood samples will be drawn in the evening. If the subject is taking ORMD-0801 460 IU bid, the PD blood samples will be drawn in the morning or evening. If the subject is taking ORMD-0801 460 IU tid or placebo, the PD blood samples will be drawn in the morning, afternoon, or evening.

Integrium, LLC will generate and implement the randomization procedures for this trial. A computer-generated randomization schedule will be used for assigning treatment (active or placebo). The Investigational Site pharmacist will follow this randomization schedule to dispense the appropriate study treatment.

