5.3.1.2 Double-Blind Treatment Administration

Study treatment (active or placebo) will be administered during Visit 2 on Days 4-8. **Prior to administering the scheduled dose of study drug, the most recent available reading on the CGM monitor must indicate a blood glucose of ≥ 70 mg/dL.** On all days, subjects will receive a dose of study treatment or placebo at approximately 7am (\pm 60 minutes), approximately 1pm (\pm 60 minutes), and a dose before bed at approximately 10 pm (\pm 60 minutes).

Subjects may be randomized to receive ORMD-0801 qd, bid, or tid:

- Subjects receiving ORMD-0801 qd will receive their dose at approximately 10pm (\pm 60 minutes), while receiving identical placebo at approximately 7am (\pm 60 minutes) and at approximately 1pm (\pm 60 minutes).
- Subjects receiving ORMD-0801 bid will receive their doses at approximately 7am (\pm 30 minutes) and before bed at approximately 10pm (\pm 60 minutes), while receiving placebo at approximately 1pm (\pm 60 minutes).
- Subjects receiving ORMD-0801 tid will receive their doses at approximately 7am (\pm 60 minutes), at approximately 1pm (\pm 60 minutes), and before bed at approximately 10pm (\pm 60 minutes).

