6.5 Pharmacokinetic/Pharmacodynamic Assessments

Blood samples for PK/PD analysis of absorbed insulin based on C-peptide correction of total insulin levels will be collected during Visit 2, Periods 1, 2, and 3, on Day 3 and Day 8. An indwelling venous catheter may be inserted for the collection of blood samples if deemed necessary. One 4.5 mL sample of total whole blood will be collected for each blood draw.

On Day 3, blood samples will be collected at the following nominal time points relative to the scheduled (per randomization scheme) dose of placebo: predose (45 to 5 mins prior to dosing) and every 30 minutes (\pm 5 minutes) postdose until 5 hours has elapsed. On Day 8, blood samples will be collected at the following nominal time points relative to the scheduled (per randomization scheme) dose of study treatment (active or placebo): predose (45 to 5 mins prior to dosing) and every 30 minutes (\pm 5 minutes) postdose until 5 hours has elapsed. The total volume collected from each subject for PK/PD samples will be approximately 99 mL per treatment Period, for a total of 297 mL during the entire study. Actual blood sampling times must be recorded in the source and eCRF.

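### The Day 8 step lists time the pre-dose PD sample to a placebo dose, which contradicts Protocol Sections 5.2 and 6.5 and cannot be applied to tid

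*Protocol*

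**What the plan says.** The Day 8 lists for the three periods are Protocol 3.3.1.6, 3.3.2.6 and 3.3.3.6. The Period 1 list reads "Collect a blood sample according to schedule (per randomization scheme, either morning, afternoon, or evening) prior to the specified dose of placebo for", and two tests are listed under it: PD analysis before the dose, and serum chemistry. The other two also place this sample "prior to the specified dose of placebo for" those tests. A separate line in each list covers the half-hourly post-dose draws up to 5 hours; it refers to the randomization scheme and does not say which kind of dose they follow. The Day 3 lists (3.3.1.3, 3.3.2.3, 3.3.3.3) carry the same two lines.

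Two other sections give a different rule for Day 8:

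- Section 5.2: "When the subject is on active therapy, the PD blood samples will be drawn after an active therapy dose (not after the placebo dummy"). It then gives the slots: evening for qd, morning or evening for bid, and any of the three for tid or placebo.
- Section 6.5 words the days separately. Day 3 draws are relative to the scheduled placebo dose. Day 8 draws are relative to the "scheduled (per randomization scheme) dose of study treatment (active or placebo").

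Footnote 7 to Table 1 says only that samples are pre-dose and post-dose, scheduled by the randomization scheme.

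Section 5.3.1.2 fixes where the dummies fall. Subjects on qd take the active dose at 10pm "while receiving identical placebo at approximately 7am" and again at 1pm. Subjects on bid take active doses at 7am and 10pm "while receiving placebo at approximately 1pm". All three tid doses are active.

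**The concern.** On Day 3 the phrase is accurate, because all doses that day are single-blind placebo. On Day 8 subjects take randomised treatment, and the dosing lines of the same list offer study treatment or placebo. A placebo dose on that day exists only in the placebo period or as a dummy, so the sampling line points away from the active dose that Section 5.2 requires.

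What is at stake is the timing of the insulin and C-peptide profiles. SAP 2.8.2 uses Day 3 as the within-subject control, takes time-matched Day 8 minus Day 3 changes, and summarises them over intervals up to 300 minutes. Those intervals are informative about uptake only if time zero is an active dose. Two secondary objectives, insulin PK and C-peptide PD, depend on this.

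**Working it through.** **Inputs.** Dose times and dummies: Protocol 5.3.1.2. Slot rule, with one morning, one afternoon and one evening period per subject: 5.2. Sampling window of 5 h: 6.5. Subjects: about 30, each on placebo plus two of three active regimens (5.2, 8.1).

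**Sampling schedule reproduced.** Draws per profile: 1 pre-dose + 300/30 post-dose = 11. Volume: 11 × 2 days × 4.5 mL = 99 mL per period, and 99 × 3 = 297 mL in all. Both agree with Section 6.5, so the draws themselves are consistent; only the index dose is in question.

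**Slots allowed under each rule on Day 8.**

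| Regimen | Active doses | Placebo doses | Slots under 5.2 | Slots if indexed to placebo |
|---|---|---|---|---|
| qd | 10pm | 7am, 1pm | evening | morning, afternoon |
| bid | 7am, 10pm | 1pm | morning, evening | afternoon |
| tid | 7am, 1pm, 10pm | none | any | none |
| placebo | none | all | any | any |

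For every active regimen that can be scheduled under both rules, the two sets of slots do not overlap.

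**Ways to allocate the three slots to one subject's three periods.**

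| Active pair | Under 5.2 | If indexed to placebo |
|---|---|---|
| qd + bid | 1 | 1 (qd morning, bid afternoon, placebo evening) |
| qd + tid | 2 | 0 |
| bid + tid | 4 | 0 |

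Section 5.2 is feasible for every pair. The literal Day 8 text is infeasible for any subject assigned tid.

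**Nominal time from the last active dose under the literal text.**

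- qd at 7am: 10pm to 7am = 9 h, and to noon = 14 h, so the window is 9–14 h.
- qd at 1pm: 10pm to 1pm = 15 h, and to 6pm = 20 h, so 15–20 h.
- bid at 1pm: 7am to 1pm = 6 h, and to 6pm = 11 h, so 6–11 h.

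Dose tolerances move these. With ±60 minutes at each end, a start can shift by up to 2 h, so the bid window could begin at 6 − 2 = 4 h and overlap the last 5 − 4 = 1 h after the active dose. Section 5.3.1.2 also gives ±30 minutes for the bid 7am dose; the start is then no earlier than 6 − 1.5 = 4.5 h, with 0.5 h of overlap. The qd windows begin no earlier than 9 − 2 = 7 h.

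**Count.** Planned active-regimen Day 8 profiles: 30 × 2 = 60. Under the literal text, 0 of 60 would have an active index dose; under 5.2, all 60 can. If allocation is balanced, which the documents do not state, that is 60/3 = 20 profiles per regimen.

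**The case against.** The strongest reply is that no one would follow the phrase. The same line takes the slot from the randomization scheme, so staff are told when to draw and need not look for a dummy. Sections 5.2 and 6.5 agree with each other, and footnote 7 to Table 1 does not mention placebo. Capsules are identical in appearance, so blinded staff could not pick out a dummy in any case. The phrase is attached only to the pre-dose PD and chemistry sample; its reach to the post-dose draws is an inference, though a natural one, since Section 6.5 times both to one dose.

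All of this stands as to likelihood, and it makes the profile count a worst case. It does not remove the contradiction. The phrase is an operative instruction repeated in three lists. The safeguard sits in a separate randomization plan (SAP 2.12), which is not available here.

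Two stronger readings are tempting, and the documents support neither:

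- A reader might infer that the literal text would compare placebo with placebo and so show no absorption. In an active period the subject has been on randomised treatment since Day 4, whereas Day 3 is all placebo, and a bid profile at 1pm nominally starts 6 h after that morning's active dose. Such a profile is mistimed for uptake; it is not a placebo–placebo contrast.
- A reader might infer that the wording pushes staff to seek the treatment assignment. The line already sends them to the scheme for the slot, so this is speculation.

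**Conclusion.** The three Day 8 lists are wrong as written and should be reconciled with Sections 5.2 and 6.5. This is a drafting inconsistency, not a flaw in the sampling design, which is feasible under Section 5.2. Its size depends on the unseen randomization plan. If the plan assigns slots by the Section 5.2 rule and the site follows them, no profile is affected. If the Day 8 text were followed literally, none of the 60 planned active profiles would be indexed to an active dose and the tid profiles could not be scheduled at all. The total of 60 assumes 30 subjects completing all periods; about 20 per regimen also assumes balanced allocation. Nothing in the documents shows that any profile would in fact be mistimed.

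**What to change.** In Protocol 3.3.1.6, 3.3.2.6 and 3.3.3.6, time the pre-dose PD and chemistry sample *prior to the scheduled dose of blinded study treatment (slot per randomization scheme)* in place of the reference to placebo. State in the next line of each list that the post-dose draws follow that same dose. Confirm that the randomization plan assigns slots by the Section 5.2 rule. Leave the Day 3 text unchanged.

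The cost is the same small wording change in three places and one check of an existing document. The number of draws, the blood volume, the blinding and the SAP analysis do not change.
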